**List of Abbreviations**

cCBT Computerised Cognitive Behavioural Therapy

CRF Clinical Research File

CTIMP Clinical Trial of an Investigational Medicinal Product

GAD- 7 Generalised Anxiety Disorder 7-item scale

GAD -2 Generalised Anxiety Disorder 2 – item scale

NHS National Health Service

NICE National Institute for Clinical Excellence

PHQ -2 Patient Health Questionnaire -2 (also known as the Whooley questionnaire)

PHQ-9 Patient Health Questionnaire -9.

PNMH Perinatal Mental Health

EPDS Edinburgh Postnatal Depression Scale.

PES Pregnancy Experience Scale

WEMWS Warwick Edinburgh Mental Wellbeing Scale

PAI Prenatal Attachment Inventory

MAI Maternal Attachment Inventory

## **1. INTRODUCTION**

### **1.1. Background**

Depression and anxiety during the perinatal period is one of the most common complications of childbearing, with a reported occurrence in 10-15% of pregnancies (1, 2). Depression in pregnancy has been linked to poorer obstetric outcomes such as an increased incidence of preterm birth, obstetric interventions such as caesarean sections, and low birth weight in infants (3). In the longer term, depression and anxiety in pregnancy have been linked with poorer cognitive and developmental outcomes for the infant (4). It is reported that women can often be reluctant to seek professional support for depressive symptoms due to social stigma, potential long waiting times for face-to-face psychological therapies and the reported uncertainties of using pharmacological interventions during pregnancy (5).

There is therefore an unmet need for an effective, low-cost, non-pharmacological intervention to help treat depressive symptoms during the perinatal period. Computerised courses based on the Cognitive Behavioural Therapy (CBT) approach have a proven evidence base as an effective and acceptable intervention for depression in a non-pregnant population and is recommended by NICE as a low-intensity psychosocial intervention for mild-moderate depression. The current NICE Guidelines pathway for Antenatal and Postnatal Mental Health signposts the practitioner to the general population guidelines when mild-moderate depression is suspected in pregnancy, however the content of generic depression sites are by very nature generic and aren't adapted to meet the needs of expectant mothers. Therefore, generic cCBT packages are being put forward as a low-intensity intervention for mild-moderate depression in pregnancy without a strong evidence base to support its efficacy in this unique population experiencing a major life event and evolving psychosocial needs (6).

Studies have highlighted that women are also increasingly turning to the internet to seek health related information in pregnancy, and many women would like health professionals to actively suggest suitable online resources (7). Advantages of the internet, including cCBT is that it can be accessed anonymously, at low cost and at a time and place convenient for the user. Although there is strong theoretical support for web-based interventions specific to supporting perinatal mental health, more evidence is required in order to fully evaluate its effectiveness.

### **1.2. Rationale for the Study**

'Enjoy Your Bump (EYB)' is an online life skills course based on CBT principles which has been designed by [name] from the University of Glasgow to specifically support women in the antenatal period. A survey of women and health professionals has demonstrated that this is a resource that both groups find acceptable. The aim of this quasi-experimental feasibility study is to evaluate the user experience and efficacy of this online programme as a non-pharmacological, low intensity intervention for women experiencing mild-

moderate depressive symptoms in pregnancy. This will be achieved by measuring depression and anxiety as well as measures of attachment to the developing baby, pre and post intervention. It is hoped the results from this study will help inform whether this is a resource that should be made more widely available to women in the NHS. It is hypothesised that the 'Enjoy Your Bump' will be an acceptable and effective intervention for women experiencing mild to moderate depressive symptoms in the antenatal period.

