## **3. STUDY DESIGN**

We propose a quasi-experimental design, in which an identified population: pregnant women with mild to moderate chronic PNMH identified with score  $\geq 2$  on PHQ-2 and/or a score  $\geq 2$  on GAD -2, and who are 16-32+6 weeks' gestation will be approached by a member of the research team and encouraged to engage with intervention (cCBT programme Enjoy Your Bump). Outcomes: an assessment of recruitment, retention and return of questionnaire data. In addition, outcome data will be measured pre-intervention, immediately post-intervention and 12 weeks postnatal.

Recruitment: Pre-screening

Women will be identified for participation in this study by three different means:

1. Answering 'yes' to one or both of the routine mental health screening question at booking with their community midwife. The two routine questions asked at a booking appointment are as follows:

*"During the past month have you often been bothered by feeling down, depressed hopeless?"*

*"During the past month have you often been bothered by having little interest or pleasure in doing things?"*

Midwife will then give participant flyer about the project, and ask if they would be happy to sign a 'consent to be contacted slip' and advise them that research team may be in touch.

2. Referred to the study by a member of the healthcare team, who has identified concerns with mental health in the antenatal period (prior to 32+6 weeks of pregnancy). Only women who have signed a 'consent to be contacted' slip will be referred.
3. Self-refer to study having received a flyer about study from a member of the healthcare team.

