#### **4.2. Inclusion/exclusion criteria**

##### **Inclusion Criteria**

- $\geq 18$  years old
- Singleton pregnancy
- Mild to moderate chronic PNMH identified with score  $\geq 2$  on PHQ-2 or GAD-2
- 16+0 – 32+6 weeks' gestation at time of recruitment.

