#### **8. STATISTICS AND DATA ANALYSIS**

## **8.2. Proposed analyses**

We will use simple descriptive statistics to describe the participant demographics.

Differences in scores from before and after the intervention will be tested using paired t-tests. Summary statistics of data obtained from the other questionnaires will be described and used as pilot data to calculate sample size for future studies.

The comments in the feedback questionnaire will be analysed using thematic analysis to identify themes within the interviews.

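### Section 1.2 sets an efficacy aim and hypothesises an effective programme, but one uncontrolled group measured before and after can show change without attributing it to the programme

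*Protocol*

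**What the plan says.** Section 1.2 gives the aim: "The aim of this quasi-experimental feasibility study is to evaluate the user experience and efficacy of this online programme". The next sentence gives the means: "This will be achieved by measuring depression and anxiety as well as measures of attachment to the developing baby, pre and post intervention". The section then hopes that the results "will help inform whether this is a resource that should be made more widely available to women in the NHS", and closes with the hypothesis that the programme "will be an acceptable and effective intervention for women experiencing mild to moderate depressive symptoms in the antenatal period".

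Section 3 describes the design: "We propose a quasi-experimental design, in which an identified population" is approached and encouraged to use the programme, and "outcome data will be measured pre-intervention, immediately post-intervention and 12 weeks postnatal". Consented women are given a code to unlock the website. No section describes a control group, a comparison cohort or any allocation. Entry under Section 4.2 is by symptom screen ("Mild to moderate chronic PNMH identified with score" of at least 2 on PHQ-2 or GAD-2).

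Section 8.2 names one test: "Differences in scores from before and after the intervention will be tested using paired t-tests".

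Section 4.1 expects substantial dropout and describes recording it as part of an efficacy test, which is a different use of that word from the one in 1.2.

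**The concern.** Efficacy and effectiveness are causal terms: they compare what happened with what would have happened without the programme. A single group measured before and after carries no information on the second half of that comparison.

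The consequence is one of interpretation. Section 1.2 connects the results to wider NHS provision. Read against the stated aim and hypothesis, a significant fall in PHQ-9 or GAD-7 would look like support for effectiveness, which the design cannot give. A non-significant change would not refute effectiveness either, because scores might have worsened without the programme. A similar risk arises later: Section 8.2 intends pilot data for sizing future studies, and an uncontrolled change carried over as a treatment difference could mis-size a controlled trial.

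**Working it through.** There is no stated power, effect size or bias figure to reproduce. The check sets the sections side by side and then asks what the protocol allows one to say about size.

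**1. Claim against design.**
- Claim (1.2): evaluate efficacy; hypothesise an effective programme.
- Design (3, 4.2): one symptom-selected group with no comparator.
- Test (8.2): paired before-after difference.
- What the test estimates: mean change among women with both measurements. That matches the third primary objective in 2.1, which attaches an effect size to changes. It does not match the efficacy aim in 1.2.

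**2. Rival explanations found in the protocol itself.**
- *Regression to the mean:* entry requires a raised PHQ-2 or GAD-2 score (3, 4.2).
- *Course of pregnancy and birth:* Section 1.1 describes a major life event with changing psychosocial needs.
- *Other care:* Section 3 provides for referral to perinatal mental health services during the study.
- *Selective follow-up:* Section 4.1 reports that about 15% in a survey-based study completed all modules and questionnaires. If that rate applied to the maximum of 120 women, 120 × 0.15 = 18 would do so. The protocol does not say that it will apply. In Section 3, the invitation to repeat the questionnaires is tied to completing the programme.

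**3. Time available for change from other causes** (in days of gestation: 16+0 = 112, 32+6 = 230, 38+0 = 266).
- Longest baseline-to-post gap, entry at 32+6: 266 − 230 = 36 days.
- Longest baseline-to-post gap, entry at 16+0: 266 − 112 = 154 days = 22 weeks. Section 3 expects the programme itself to take 5–8 weeks.
- Baseline to 12 weeks postnatal, assuming birth at 40+0 (280 days): from 280 + 84 − 230 = 134 days (19 weeks 1 day) to 280 + 84 − 112 = 252 days (36 weeks). Earlier births shorten this and later ones lengthen it. Every such comparison spans the birth.

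**4. Can the bias be sized?** Take regression to the mean alone, with normal scores, one screen and zero programme effect. The expected change, in SDs of the unselected score, is (r_screen,baseline − r_screen,post) × λ, where λ = φ(k)/p, p is the share passing the screen and k is the normal cut-off for that share. None of these inputs is in the protocol. Under assumed values:
- equal correlations: 0 × λ = 0;
- correlations 0.8 and 0.7, 80% passing (λ = 0.350): 0.1 × 0.350 = 0.035 SD;
- correlations 0.8 and 0.5, 20% passing (λ = 1.400): 0.3 × 1.400 = 0.42 SD.

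The answer runs from nothing to 0.42 SD according to the assumptions, so no figure is claimed. The number of women does not enter the formula: recruiting more would not remove the shift, and a confidence interval would be displaced as much as a p-value.

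**The case against.** The best reply is that the operative sections are already those of a feasibility study. The aim sentence itself uses the word. The primary objectives in 2.1 are recruitment and retention, acceptability, and an effect size for changes. The endpoint in 2.2 is completion of study steps, and 8.2 speaks of pilot data. No objective or endpoint tests efficacy, there is no success criterion or significance level, and the sentence on NHS availability is only a hope. Nor does 1.2 say that the hypothesis will be tested by the before-after scores: the statement of means attaches to the aim, and the hypothesis follows later. Section 4.2 also excludes women already in psychological therapy, and women recruited through booking are in effect screened twice, so some regression may precede baseline.

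Much of this stands, and it limits the point in four ways:
- A reader might infer that the paired t-test is the wrong analysis. It is not; it suits the changes named in 2.1.
- A reader might infer that the study will declare effectiveness on a significant p-value. No section says so.
- A reader might fault the third primary objective as ambiguous. It already speaks of changes, in a study with no second group.
- A reader might want scale-by-scale intervals and a comparison of women with and without follow-up. Those are commonly left to a statistical analysis plan, and their absence here is no finding.

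What does not stand is that nothing needs changing. The aim and hypothesis are current text, they go beyond the objectives, and no section warns that change cannot be attributed to the programme. The exclusion and the repeated screen reduce the rival explanations without removing them. An analysis plan cannot supply a comparator.

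**Conclusion.** The point holds as a mismatch between the claim in 1.2 and the design, and it should be corrected. It rests on the protocol's own wording and on the absence of any described comparator, not on an assumed bias. The assumed inputs above give anything from 0 to 0.42 SD for regression to the mean alone, so neither the presence nor the size of bias in this study can be stated. It would be too strong to say that an observed change must be spurious, or that the study is unfit for its purpose. Recruitment, retention and acceptability can be assessed as planned, and within-woman change can be described and tested. Only the step from change to efficacy is unsupported.

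**What to change.** - **Section 1.2:** restate the aim and hypothesis in terms of feasibility, acceptability and observed within-woman change, and remove the words *efficacy* and *effective*.
- **Section 4.1:** replace the phrase that treats dropout recording as an efficacy test with wording on engagement and retention.
- **Section 8.2:** add one sentence, for example: *Before-after tests and estimates are exploratory, describe uncontrolled change, are not evidence of efficacy, and should not be used as a between-group effect when a future controlled trial is sized.*

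This costs wording only: no extra women, visits or data. The downside for the sponsor is that the report cannot claim effectiveness from a significant before-after change; that question is left to a controlled study.

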## **2. STUDY OBJECTIVES**

### **2.1. Primary and Secondary Objectives**

Primary Objectives:

- i) Evaluate recruitment and retention to study and return of questionnaire data.
- ii) Evaluate feedback questionnaire data to assess acceptability of intervention.
- iii) Obtain an estimate of effect size for changes in anxiety, depression, social function and attachment to the developing baby.

Secondary Objectives:

[figure not shown]
- i) Measure depression (PHQ-9, EPDS, PES, WEMWS) anxiety (GAD-7) scores before and after the intervention (immediately post-intervention and 12 weeks postnatal)
- ii) Evaluate Mother-baby relationship and attachment using PAI before and after intervention and MAI at 12 weeks postnatal.
- iii) Measure pregnancy-experience pre and post intervention.
- iv) Test the ability to deliver and support the intervention, and quantify how long it typically takes women to complete the intervention.

### **2.2. Primary and Secondary Endpoints**

- i) Completion of verbal screening, baseline scores, intervention (Enjoy Your Bump), post intervention questionnaire and 12-week postnatal follow-up questionnaires.

## **3. STUDY DESIGN**

We propose a quasi-experimental design, in which an identified population: pregnant women with mild to moderate chronic PNMH identified with score  $\geq 2$  on PHQ-2 and/or a score  $\geq 2$  on GAD -2, and who are 16-32+6 weeks' gestation will be approached by a member of the research team and encouraged to engage with intervention (cCBT programme Enjoy Your Bump). Outcomes: an assessment of recruitment, retention and return of questionnaire data. In addition, outcome data will be measured pre-intervention, immediately post-intervention and 12 weeks postnatal.

Recruitment: Pre-screening

Women will be identified for participation in this study by three different means:

1. Answering 'yes' to one or both of the routine mental health screening question at booking with their community midwife. The two routine questions asked at a booking appointment are as follows:

*"During the past month have you often been bothered by feeling down, depressed hopeless?"*

*"During the past month have you often been bothered by having little interest or pleasure in doing things?"*

Midwife will then give participant flyer about the project, and ask if they would be happy to sign a 'consent to be contacted slip' and advise them that research team may be in touch.

2. Referred to the study by a member of the healthcare team, who has identified concerns with mental health in the antenatal period (prior to 32+6 weeks of pregnancy). Only women who have signed a 'consent to be contacted' slip will be referred.
3. Self-refer to study having received a flyer about study from a member of the healthcare team.

Answering 'yes' to one or both routine mental health screening questions at booking (approximately 8-11 weeks of pregnancy), will prompt the community midwife to give a flyer to the woman giving an overview of the study. They will ask women if they are happy to sign a 'consent to be contacted' slip. If the woman is happy to do so, the midwife will advise the woman that a member of the research team may approach them. The flyer will also contain contact information if potential participants wish to contact the research team themselves. Our research midwives manage two specialist antenatal clinics on behalf of the NHS (Obesity and preterm birth clinic). They are an essential part of the overall NHS Lothian team caring for women in pregnancy. Each hold an honorary contract with NHS Lothian and ensure they meet the standards required by the Trust to support and care for women during pregnancy. As a member of the clinical care team to whom the patient has been referred or directly in their capacity as a researcher they may approach women within the maternity setting to participate in research.

[figure not shown]
A member of the research team will personally approach these women who have consented to be contacted when they attend for their booking scan and ask if they would be interested in taking part. Alternatively, potential participants will be contacted via telephone by a member of the research team following their first scan. If potential participants are interested in participating they will be given a participant information sheet (either in person or via post).

Alternatively, women may be referred to the study by a member of the healthcare team, who has identified concerns with mental health in the antenatal period (prior to 32+6 weeks of pregnancy). In this instance, a member of the healthcare team will give a flyer giving an overview of the study to the woman, and ask if she would be willing to sign a 'consent to be contacted' slip. They would then make a referral to the research team who will then meet with the woman or contact the woman via telephone to gauge interest, answer any questions and invite for pre-screening. A patient information sheet shall be given/sent out in the post.

Prior to invitation to attend for the first visit for this project, interested volunteers will be assessed for eligibility to take part in this study by being asked by the researcher either face to face in the antenatal clinic setting or over the telephone, the two questions in the PHQ-2 and GAD-2 questionnaires. Those who score  $\geq 2$  on either questionnaire will be eligible for

study and invited to meet the researcher for consent and first visit. The PHQ-2 and GAD-2 are short, standardised screening tools that identifies people at highest risk of depression. Those who are ineligible will be thanked for their time and given an information leaflet signposting them to appropriate perinatal mental health support. This will either be given in person, or if screening occurs over the phone this leaflet will be sent in the post.

Women will be at least 16+0 and less than 32+6 weeks pregnant when they attend to consent to this study. The meeting will take place in a clinical setting within Lothian which is most convenient for the woman to travel to. During the first visit the following process will occur:

## Study

Consented participants will:

- i) Complete questionnaires to obtain baseline scores. They will be asked to complete:
  - a. Patient Health Questionnaire – 9( PHQ-9)
  - b. Edinburgh Postnatal Depression Score (EPDS)
  - c. Pregnancy Experience Scale (PES)
  - d. Warwick Edinburgh Mental Wellbeing Scale (WEMWS)
  - e. Prenatal Attachment Inventory (PAI)
  - f. Generalized Anxiety Disorder 7-item scale (GAD-7)
- ii) The participant will then be allocated a unique code to unlock access the EYB website. They will register to the website with the help and support of a member of the study team who will ensure the participant understands the website and can navigate to the five core 'Change Modules' which they will need to complete as part of the intervention. Each module takes the form of an online slideshow with audio. Participants work through the slides at their own pace. There is no data input required from them to complete the module. Each module has worksheets that accompany the content. Participants will be given all the worksheets at this first session. These worksheets are for participants own reference and do not need to be seen by the research team. Before leaving the session, participants will be given a leaflet signposting them to further perinatal mental health support.
- iii) The participant will have up to 38+0 weeks gestation to work through and complete the five modules and accompanying worksheets. During this time, participants will be offered ongoing support from a Research Midwife in the form of phone call and/or text message no more frequently than once weekly. We anticipate that the intervention will take about 5-8 weeks to complete.
- iv) On completion of the intervention, (up to 38+0 weeks gestation) participants will be invited to attend to repeat all measurements of assessment obtained prior to the intervention. This can be gathered either face to face or via telephone. . In addition, participants will be asked to complete an anonymous evaluation questionnaire online detailing their experience of the intervention.
- v) 12 weeks following the birth of their baby, participants will be invited to complete all questionnaires other than the PES and PAI for the final time. The MAI will be used to assess attachment. These measures shall be collected face to face or via telephone.

The volunteers will be thanked for their participation in the study. The participant data collected will be coded and anonymised.

During the study, if the researcher has any concerns regarding the mental wellbeing of participants they will respond using the standard risk management protocols used in NHS Lothian and make the appropriate referrals in consultation with the participant. In this instance, a member of the research team will also contact the woman's named midwife and/or obstetrician to discuss and make them aware of the concerns. After consultation, if thought appropriate, a referral would be made to perinatal mental health services and/or contact made with the woman's GP. At the screening phase of the study participants will be given a leaflet detailing further mental health support available.

